If a participant is unable to read, an impartial third party witness will have to be present during the consent process to confirm that the process has taken place. The consent document must be read to the participant and the process documented in the research file. The participant will "make their mark" (f.ex. thumbprint) on the signature section of the consent document, in order to document their understanding. Both the witness and the person obtaining informed consent. Both the witness and the person obtaining informed consent must also sign and date the consent.

RCT Treatment randomization: After obtaining written, informed consent and following all screening and study baseline procedures, individuals in the RCT will be randomized on a 1:1 basis to participate in either TEAM or ETAU. Block randomization with block sizes ranging randomly between 4 and 8 consecutive patients will be employed to ensure that equal numbers of TEAM and ETAU patients occur within strata and are balanced with respect to relevant comorbidity (diabetes and previous stroke). The randomization list will be computer-generated by personnel within the biostatistics core of the CWRU Neurological and Behavioral Outcomes Center who are not members of the study staff.

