Measures: Demographic variables and existing medical burden (assessed with the self-reported Charlson Index⁷⁹) will be evaluated at baseline, prior to study randomization. Baseline medical status will also be evaluated with personal and family stroke history as well as currently prescribed medications. Primary outcome of the RCT will be change in systolic BP from baseline to 6-month follow-up. Additional outcomes of interest will include diastolic BP, cholesterol/lipids and glycosylated hemoglobin (HbA1c) (approximately 5mL of blood is drawn per blood draw), body mass index (BMI), measures that evaluate diet, activity levels, substance use, self-efficacy, stroke knowledge, stress, medication adherence, medication access and health resource use. Quantitative measures will be repeated at 13-week and 24-week (6-month) follow-up except for laboratory testing, which will be conducted only at baseline and 24-week follow-up. Qualitative evaluation will be conducted at baseline and at 13-week follow-up.

[figure not shown]
Primary outcome: The primary study outcome is systolic BP measured at baseline, 13-week, 24-week (6 month). All BP measurements will adhere to a standardized procedure previously used by this study team.³⁰ Prior to BP measurement study participants will be requested beforehand to refrain from smoking and drinking alcohol or caffeinated beverages at least half an hour before the examination. BP will measured with an Omron automated sphygmomanometer model HEM 907 whose accuracy has been validated.⁸⁰ The participant will be asked to sit on a chair and rest quietly for 15 minutes with his/her legs uncrossed. The left arm will then be placed on a table with the palm facing upward and the ante-cubital fossa at the level of the lower sternum. Two arm cuffs that fitted arm circumferences 9-13 inches and 13-17 inches will be available for use in BP measurement. Three measurements will be taken at least 5 minutes apart. The average of the last two readings will be considered as the final blood pressure reading.

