TEAM: Similar to previous self-management approaches developed by these investigators^{16, 31, 33} TEAM is informed by principles of social cognitive theory.⁷⁶ TEAM uses nurses and peer educator dyads (PEDs) composed of patients and their care partners to co-deliver an intervention intended to help reduce future stroke risk (Figure 1). Team begins with one 60-minute 1:1 orientation session, in which the nurse and PED meet with the patient and his/her care partner. This is followed by 6 hour-long group sessions with 6-8 patients and their care partners held approximately weekly. The first orientation session will be done approximately 1 week post baseline, followed by group sessions were done at 2, 4, 6, 8, 10 and 12 weeks post-baseline. Our pilot work suggests that the timing and format of the groups is highly acceptable to participants, with robust attendance/retention. Individuals who miss a group session are encourage to complete a make-up session conducted immediately before or after regularly scheduled groups. In cases where logistic barriers prevent in-person attendance, participants may conduct make-up sessions by phone with the nurse educator. To reinforce learning after the TEAM group sessions are done, 3 brief (approximately 10-20 minute) monthly telephone calls occur between the nurse and the patient over the next 3 months. These calls support ongoing self-management and facilitate linkage with other care providers. All TEAM participants continue in treatment with their regular medical care providers and TEAM visits will take place in these clinics.

Figure 1: TEAM participants and interactions

*Patient care partner also encouraged to participate if available

TEAM Curriculum: Topic content is noted below. In the RCT, content is delivered in 6 sessions.

Session 1: Orientation and introductions, Emphasize ground rules, Establish a therapeutic relationship, Discuss facts and myths about stroke, Overview and interactive discussion of stroke risk factors

Session 2: Medications to manage complications and reduce future risk, Nutrition for best physical and emotional health, Healthy cooking and use of salt in food preparation

Session 3: Problem-solving skills and the IDEA approach (Identify the problem, Define possible solutions, Evaluate the solutions, Act on the best solution), Effects of exercise, smoking and other substances in recovery

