Session 4: Medication routines, acknowledgement of group progress, self-management and recovery as a lifestyle.

Session 5: The importance of having a regular healthcare provider, Talking with health care providers, Working with traditional healers

Session 6: A personal care plane to take care of the body and mind, Acknowledgement of group progress, Self-management and recover as a lifestyle

Training for TEAM: The team will hire and train up to 8 nurses and up to 12 PEDs. Training will follow the same procedures as in the TEAM Uganda pilot and in past self-management trials.⁷⁷ Initial training will be a 2-day intensive to review the TEAM curriculum followed by training /support sessions monthly during year 1, at least quarterly thereafter, attended by clinical research staff, nurses and PEDs.

ETAU: ETAU will consist of an orientation visit (approx. 30 minutes) with a nurse who will provide patient-education materials on stroke risk adapted from the American Heart Association materials and cover common risk factors such as hypertension, obesity, high salt/high fat diet and diabetes. This visit will take place in the outpatient clinic where patients get their medical care. Patients will also receive basic written information in their language of preference and tailored to the reading level of most patients at the clinic. Patients will be offered the opportunity to bring a family member with them to this visit who may also ask questions and who can assist them with understanding written materials for those with limited literacy. To control for the same number of patient contacts as TEAM, the nurse in ETAU will then follow-up with participants with a series of 9 brief phone calls spaced out over the course of 6 months (approximately every 2 weeks during months 1 and 2, then approximately monthly thereafter). Content will reinforce materials provided in the orientation visit and the nurse will be available to answer questions that may arise. Different nursing personnel will deliver the TEAM and ETAU interventions to minimize chance of contamination across study arms.

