Quantitative data Analysis: Preliminary descriptive analyses will examine change over time in systolic BP as well as secondary outcomes. The measures of interest are valid and reliable, and have been used in stroke studies in the SSA setting.^{24, 30, 88, 97, 98} Primary and secondary outcome measurements will be assessed at baseline prior to randomization to either TEAM or ETAU, and at the 13 week and 6 month time-points using the same methods as in our pilot work. Of primary interest is the treatment by time interaction in systolic BP, measured from baseline to 6 months after randomization between TEAM and ETAU. Explanatory variables will include age, gender, stroke history and rural vs. urban status.

The 13-week systolic BP measurement will reflect the period following baseline (when individuals participating in TEAM Uganda will have just completed the “intensive” group sessions), and it will be used to assess for within-subject differences from baseline to 13 weeks and 13 week to 6-month time periods. This will allow for a greater understanding of the time course for when the expected reductions occur in the TEAM Uganda group, which we expect to mostly occur after the “intensive” group sessions have ended. We will analyze change from baseline to 13 weeks as well, analyzing contrasts within the mixed model framework.

For aim 2, we will use 2 group by 3 time waves repeated measures analysis of variance (RMANOVA) for each of the 3 hypotheses in Aims 2. These analyses will compare two groups (TEAM intervention vs. enhanced treatment as usual (ETAU)) across three time waves of systolic BP (H1), serum cholesterol (H2), and serum HbA1c (H3). When using a repeated measures ANOVA, it not only assesses mean differences across time, but also assesses group differences, as well as, the interaction of time X group which will allow us to test the trend of the means over time across the three groups. The repeated measures ANOVA, not only can be used to determine if there are mean differences across the three time periods, it can also utilize orthogonal polynomial contrasts to determine linear and quadratic trends of the means across time. Orthogonal polynomials are weights

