Sample size calculations: From our pilot data, mean baseline systolic BP was 162.9 (SD 25.6). Change from baseline to 6 months with the TEAM Uganda intervention saw a mean systolic BP of 149.7 (SD 22.1). Reductions BP of ≥ 2 mm Hg can significantly reduce the incidence of cardiovascular disease and its complications in both hypertensive and normotensive individuals, and reductions of the magnitude seen in this team's pilot work is well above thresholds that are considered clinically meaningful.^{94, 95} Our projected sample size is n=246, with 123 participants per arm. Based on our preliminary mixed model, we observed difference in systolic BP from baseline to 24 weeks of 13.22, with standard deviation of 25.84, and within subject correlation parameter value of 0.57. However, we will conservatively estimate our sample size based upon a difference of 10 mmHg, commensurate with a meta-analysis that used this magnitude of change in BP across a large sample with varying baseline blood pressure levels and comorbidities.⁹⁶ Also in our pilot work with the TEAM Uganda study, we observed an attrition rate of 12.5% at 6-months follow-up. Conservatively, for this study, we will assume 25% attrition. Finally, to assume for two-sided test of time-by-treatment group interaction, Type I error level is 0.05. Then, in a linear mixed model with subject-level and center-level random effects, power is 0.80 for a clinically significant difference of 10.0 mm Hg between treatment arms for the projected sample size of 246 subjects in total. We should thus have sufficient power. We do assume compound symmetry over the 3 time periods. We will also consider an AR(1) covariance model, and compare model fits.

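### TEAM is delivered in groups of 6-8 and ETAU is not, but neither the H1 analysis nor the power model has a TEAM-group term, so the 0.80 rests on an unstated ICC of zero

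*Combined protocol and SAP*

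**What the plan says.** Under RCT Treatment randomization, "individuals in the RCT will be randomized on a 1:1 basis to participate in either TEAM or ETAU". The TEAM section then describes a 1:1 orientation followed by "6 hour-long group sessions with 6-8 patients and their care partners held approximately weekly", co-delivered by a nurse and a peer educator dyad, with monthly nurse calls afterwards. On missed sessions it says: "Individuals who miss a group session are encourage to complete a make-up session conducted immediately before or after regularly scheduled groups". A phone make-up is allowed where attendance is impractical.

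The ETAU section describes one orientation visit with a nurse, after which "the nurse in ETAU will then follow-up with participants with a series of 9 brief phone calls". No ETAU group sessions are described. That ETAU is delivered to individuals is therefore a reading of the section, not its stated wording.

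For Aim 2, the Data Analysis Plan names a "2 group by 3 time waves repeated measures analysis of variance (RMANOVA) for each of the 3 hypotheses", with age, gender, stroke history and rural or urban status as explanatory variables. Mixed models may also be explored for contrasts. The Sample size calculations state that "in a linear mixed model with subject-level and center-level random effects, power is 0.80" for 10 mmHg with 246 subjects. They assume 25% attrition, although in the pilot "we observed an attrition rate of 12.5% at 6-months follow-up".

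No section mentions a term for TEAM session group, an ICC, a design effect, or an assumption that clustering by group is zero.

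**The concern.** Individual randomisation followed by group delivery in one arm gives a partially nested design. Patients who share a group also share a nurse, a peer dyad and one another's influence. If that makes their 6-month changes more alike than those of patients in different groups, the TEAM mean is less precise than 92 independent patients would make it. An analysis without a group term then understates the standard error.

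The center effect in the power model cannot stand in for a group term. With 123 TEAM patients in groups of 6 to 8 there are about 15 to 21 groups, or 5 to 7 per center on average over 3 centers. ETAU patients share those centers but not the groups.

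At stake are the width of the H1 interval, the meaning of the stated 0.80 and, in one particular situation, the type I error. If group membership is not recorded, none of this can be checked afterwards.

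**Working it through.** **Inputs from the Sample size calculations:** SD 25.84, within-subject correlation 0.57, difference 10 mmHg, two-sided 0.05, 123 per arm, 25% attrition, compound symmetry. **From the TEAM section:** groups of 6-8. **Assumed:** ICC of 6-month change 0.01, 0.02 and 0.05, with 0.10 as a stress case; average group of 7; attrition spread evenly over groups; equal total variance of change in both arms.

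**1. Reproduce the plan's figure.** SD of change = 25.84 × √(2 × (1 − 0.57)) = 23.96. Completers per arm = 123 × 0.75 = 92.25. SE = 23.96 × √(2/92.25) = 3.528. Power = 0.809 (normal) or 0.805 (t). So 0.80 is reproduced with no allowance for groups.

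**2. Groups.** 123/8 = 15.4 and 123/6 = 20.5. Completers per group = 7 × 0.75 = 5.25, giving 92.25/5.25 = 17.6 groups.

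**3. Effect of an ICC.** The TEAM design effect is DE = 1 + (5.25 − 1) × ICC. True SE = 23.96 × √((DE + 1)/92.25). Type I error under a zero average effect = 2 × (1 − Φ(1.96 × 3.528/SE)), and coverage is its complement. Power (normal) = Φ(10/SE − 1.96). For the Satterthwaite version, the TEAM variance has 17.6 − 1 df and the ETAU variance 92.25 − 1, with noncentral-t power.

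| ICC | DE | SE | planned SE too small by | coverage | type I error | power, normal | df | power, Satterthwaite |
|---|---|---|---|---|---|---|---|---|
| 0 | 1 | 3.528 | 0 | 95.0% | 0.050 | 0.809 | 56.1 | 0.795 |
| 0.01 | 1.0425 | 3.566 | 1.0% | 94.8% | 0.052 | 0.801 | 54.5 | 0.787 |
| 0.02 | 1.085 | 3.603 | 2.1% | 94.5% | 0.055 | 0.793 | 53.0 | 0.778 |
| 0.05 | 1.2125 | 3.711 | 4.9% | 93.8% | 0.062 | 0.769 | 49.1 | 0.752 |
| 0.10 | 1.425 | 3.885 | 9.2% | 92.5% | 0.075 | 0.730 | 44.1 | 0.711 |

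With 4.5 to 6 completers per group, the planned SE is too small by 0.9 to 1.2% at ICC 0.01 and 4.1 to 5.7% at ICC 0.05. Groups that kept all 8 members would give 7.8% at ICC 0.05.

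**4. Check on the plan's own test.** The setting was 30,000 simulated trials with 18 TEAM groups, three visits, 25% random dropout and a zero average effect. The group-by-time F test rejected at 0.0500 / 0.0513 / 0.0549 / 0.0632 / 0.0774 for ICC 0 / 0.01 / 0.02 / 0.05 / 0.10, in line with the closed form. When the correlation was shared by both arms at ICC 0.02 / 0.05 / 0.10, it rejected at 0.0485 / 0.0460 / 0.0438: no inflation.

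**5. Pilot attrition.** At 12.5%, completers are 107.6 per arm and 6.125 per group. Satterthwaite power is 0.834 / 0.807 / 0.761 at ICC 0.02 / 0.05 / 0.10, and falls to 0.80 at ICC about 0.057.

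**6. Cost of a group term.** In the same simulations, a partially nested test on the 6-month change has power 0.794 at a true ICC of 0, against 0.802 without the term. If the group variance estimate may not go below zero, power is 0.774.

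**The case against.** Four points weigh against the concern.

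- **Type I error.** If the sessions change nobody's BP, they induce no correlation and the planned test holds 0.05. The 0.052 to 0.062 arises only when group effects differ but average zero, so that some groups get worse. A reader might infer that the trial's type I error is inflated in general; the documents do not support that. This objection stands. It does not touch coverage or power when TEAM works.
- **Size of the ICC.** It is wholly assumed. ICC 0.05 means true group mean changes with SD 23.96 × √0.05 = 5.4 mmHg, so 95% of groups would span roughly 0 to 20 mmHg around a 10 mmHg mean. One curriculum, fidelity checks on 20% of sessions, make-up sessions, 1:1 calls and an endpoint about three months after the last session all argue for something smaller. This stands as a reason to call the effect modest. It is not evidence that the ICC is zero.
- **Power.** A reader might infer that the 0.80 is miscalculated or that more patients are needed. Neither follows. The figure reproduces, and the plan has margin in assuming 25% attrition against 12.5% in the pilot. About 1 point of each drop in the Satterthwaite column comes from the change of df (0.795 against 0.805 at ICC 0), not from clustering.
- **The remedy can be conservative.** If the correlation is shared by both arms, for example through enrolment period, a TEAM-only group term rejects at 0.045 / 0.036 / 0.027 for ICC 0.02 / 0.05 / 0.10, below the planned test's 0.0485 / 0.0460 / 0.0438. The documents do not show which case applies. This stands and is the reason for the sensitivity analyses. A full three-visit model with separate group effects at each visit was not simulated for type I error or power, and is more than the 6-month contrast needs.

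**Conclusion.** The omission is real, and its effect is conditional and modest. The design is partially nested, and neither the H1 analysis nor the power model allows for it. If the sessions induce an ICC of 0.01 to 0.05 in 6-month systolic BP change, with about 5.25 completers per group, the H1 standard error is about 1 to 5% too small and coverage about 94.8 to 93.8%. At ICC 0.01 to 0.02 this is close to negligible. Inflated type I error is confined to a zero average effect with real differences between groups, and is absent if no group is affected or the correlation is shared equally with ETAU. The 0.80 is correct for ICC zero and should say so. This is a cheap improvement, not a flaw that threatens the trial. No size is claimed for H2 or H3.

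**What to change.** - **Data.** Record each TEAM participant's group of assignment with the attendance already collected.
- **H1 analysis.** For the baseline-to-6-month contrast, pre-specify a mixed model with a TEAM-only group random effect, ETAU participants as singletons, and small-sample df. Fit it to the 6-month change, or use a group effect specific to the 6-month visit. State a fallback for non-convergence, for example the 6-month change with a cluster-robust SE and small-sample correction.
- **Sensitivity analyses.** Report the planned model without the group term, and a version with an enrolment-period-within-center term in both arms.
- **Power statement.** Keep n=246. Give power for 10 mmHg at 25% attrition with its ICC and one named method: about 0.80 / 0.79 / 0.77 at ICC 0.01 / 0.02 / 0.05 from the design effect alone (normal approximation, 0.81 at ICC 0), or 0.79 / 0.78 / 0.75 with Satterthwaite df (0.795 at ICC 0).

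The cost is some SAP wording and one ID field (a second for enrolment period if it is not already derivable from dates), with no extra patients. The price is a slightly wider H1 interval, a slightly lower stated power, and about 1 point of power if the true ICC is 0 (0.794 against 0.802), or up to about 3 points if the group variance is bounded at zero (0.774).

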Aim 2: To conduct an RCT comparing efficacy of TEAM vs. enhanced treatment as usual (ETAU) in 246 Ugandans (TEAM, N= 123; ETAU, N= 123) at high risk for stroke. Phase 2 consists of an RCT using a Type 1 hybrid effectiveness-implementation design, which rigorously tests the clinical intervention and secondarily gathers data to inform subsequent implementation efforts and research. The RCT will evaluate key primary (systolic BP) and secondary (biological and behavioral) outcomes indicative of stroke risk. H1: Individuals in TEAM will have significantly reduced systolic BP compared to individuals randomized to ETAU. H2: Individuals randomized to TEAM will have greater reductions in serum cholesterol compared to ETAU. H3: Individuals with diabetes randomized to TEAM will have improved glycemic control as measured by serum HbA1c compared to ETAU. Secondary outcomes also include other biomarker variables, stroke knowledge and attitudes, medication adherence and health resource use. We will also explore associations of age, gender, urban vs. rural residential status and stroke history (prior vs. no previous stroke) on TEAM outcomes.

Aim 3: Identify barriers and facilitators to TEAM implementation in order to inform subsequent scale-up and spread using qualitative methods and guided by an implementation conceptual model. As with Aim 1, Aim 3 evaluation will be guided by an i-PARIHS framework. Finally, the project will grow research capacity in stroke risk reduction, training the next generation of brain health investigators in SSA. The project will help establish a sustainable infrastructure that will facilitate future scale-up of TEAM in Uganda. Taken together, the proposed project has substantial public health importance and will provide the prerequisite data and infrastructure needed to help with reducing stroke burden in Uganda and other LMIC countries across the globe.

Study Design

The proposed project is a prospective, randomized effectiveness-implementation trial of TargEted MAnageMent Intervention (TEAM. N= 123) vs enhanced treatment as usual (ETAU, N=123) in Ugandans who are at risk for stroke or have had a stroke within the last 5 years.

Study Procedures

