5. **Data and Safety Monitoring Board (DSMB) and safety review plan:** We recognize the need for careful, expert external data and safety oversight to ensure the wellbeing of the participants in this study and the scientific integrity of the project. These experts, who are not members of the study team, will review and evaluate the accumulated data for participant safety, adverse events, study conduct and progress, at minimum, every 12 months. Ad-hoc meetings might be called to evaluate unanticipated serious adverse events or any other urgent issues that are relevant and which might occur during the course of the study. The DSMB will be comprised of two clinicians with stroke expertise at the Uganda site; a faculty member/clinician with stroke expertise at the US site, and a biostatistician at the US site who are all not part of the study team, but have extensive experience with federally funded research. The DSMB communication and oversight will be accomplished via telephone, SKYPE, or email communication for issues that need more immediate attention.

The PIs will review study progress and safety regularly as described above. As noted above, progress reports, including patient recruitment, retention/attrition, and adverse events will be provided to the DSMB at least annually for independent review. The annual report will include a list and summarization of adverse events. In addition, the annual report will address (1) whether adverse event rates are consistent with pre-study assumptions; (2) reason for dropouts from the study; (3) whether all participants met entry criteria; (4) whether continuation of the study is justified on the basis that additional data are needed to accomplish the stated aims of the study; and (5) conditions whereby the study might be terminated prematurely. There will be an interim analysis conducted once half of all trial participants have completed the 6-month outcome evaluation point. The annual report will be signed by the PI/designate and will be forwarded to the DSMB. The DSMB will review the annual plan on all 5 points outlined above, as well as the interim analysis, and make recommendations to the appropriate regulatory agencies (IRB, NIH) concerning continuation, modification or termination of the study. The PI will provide a copy of all DSMB reports to the appropriate IRB and NIH on an annual basis.

Data Analysis Plan

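### Does the half-way interim analysis, which has no stated stopping rule, undermine the 0.05 significance level and 0.80 power?

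*Combined protocol and SAP*

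**What the plan says.** The interim appears once, in item 5 (Data and Safety Monitoring Board and safety review plan) under Provisions to Monitor the Data to Ensure the Safety of Research Participants: "There will be an interim analysis conducted once half of all trial participants have completed the 6-month outcome evaluation point". The same item says that the external experts will "review and evaluate the accumulated data for participant safety, adverse events, study conduct and progress" at least every 12 months.

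The annual report to the board must address five points: adverse event rates, dropouts, entry criteria, point (4), which is "whether continuation of the study is justified on the basis that additional data are needed to accomplish the stated aims of the study", and point (5), the conditions for ending the trial early. Then: "The DSMB will review the annual plan on all 5 points outlined above, as well as the interim analysis", and it makes recommendations "concerning continuation, modification or termination of the study".

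Elsewhere, Aim 2 states the main hypothesis: "H1: Individuals in TEAM will have significantly reduced systolic BP compared to individuals randomized to ETAU". Measures states: "Primary outcome of the RCT will be change in systolic BP from baseline to 6-month follow-up". The Sample size calculations paragraph assumes a "two-sided test of time-by-treatment group interaction, Type I error level is 0.05", with power 0.80 for a 10 mm Hg difference, N=246 and 25% attrition. The Data Analysis Plan does not mention the interim.

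**The concern.** Three features look troubling together. The interim is triggered by the visit at which the primary outcome is measured. It is listed in addition to five report points that already cover adverse events, dropouts and entry criteria, so a reader may ask what is left for it to examine except the outcome. And it feeds a recommendation that can include termination, while point (4) links continuation to the need for more data on the aims.

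If the board compared systolic BP between arms and could stop on the result, the single-test figures would not be safe. Stopping because TEAM already looks better, with no adjusted boundary, raises the false-positive rate above 0.05. Stopping because success looks unlikely lowers power. The plan gives no rule from which either effect could be worked out.

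**Working it through.** **1. Reproduce the plan's power as a single-look design.** Inputs from Sample size calculations: SD 25.84, within-subject correlation 0.57, compound symmetry, difference 10 mm Hg, 123 per arm, 25% attrition, two-sided 0.05.

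- SD of change = 25.84 × √(2 × (1 − 0.57)) = 23.96.
- Evaluable per arm = 123 × 0.75 = 92.25.
- Standard error = 23.96 × √(2/92.25) = 3.53; drift = 10/3.53 = 2.83.
- Power = Φ(2.83 − 1.96) = 0.809.
- With the t distribution, 92 per arm are needed; 92/0.75 = 122.7, rounded up to 123 per arm, or 246 in total.

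So 0.80 and N=246 are figures for one final test, with no allowance for an interim.

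**2. Information at the interim.** The interim could come at half the final information (t = 0.50). It could also come at 123 completers out of those expected: 123/(246 × 0.875) = 0.571 with the pilot's 12.5% attrition, or 123/(246 × 0.75) = 0.667 with the assumed 25%. Information is taken as proportional to 6-month completers. The interim and final statistics Z1 and Z2 are bivariate normal with correlation √t, and the test is of the single baseline-to-6-month contrast.

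**3. Safety and conduct look.** Systolic BP by arm plays no part in stopping, so type I error stays at 0.05 and power at the stated 0.80 (0.809 as recomputed).

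**4. Efficacy stop, final test left at 0.05.** With c the interim critical value, type I error is 1 − P(Z1 < c, |Z2| < 1.96) for a stop in favour of TEAM only, and 1 − P(|Z1| < c, |Z2| < 1.96) if a crossing in either direction counts. The thresholds are assumed, since the documents give none.

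| Interim threshold (two-sided p) | Favouring TEAM only, t = 0.50 / 0.571 / 0.667 | Either direction, t = 0.50 / 0.571 / 0.667 |
|---|---|---|
| 0.05 | 0.0666 / 0.0653 / 0.0635 | 0.0831 / 0.0806 / 0.0770 |
| 0.01 | 0.0523 / 0.0519 / 0.0513 | 0.0546 / 0.0537 / 0.0526 |
| 0.001 | 0.0501 / 0.0501 / 0.0500 | 0.0502 / 0.0501 / 0.0501 |

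**5. Futility stop, final test at 0.05.** Power is P(Z1 > f, Z2 > 1.96), with f the futility cut-off. Drift 2.80 corresponds to a power of exactly 0.80; drift 2.83 comes from the plan's own inputs. These thresholds are also assumed.

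| Stop if | Drift 2.80, t = 0.50 / 0.571 / 0.667 | Drift 2.83, t = 0.50 / 0.667 |
|---|---|---|
| Conditional power under the observed trend < 20% | 0.741 / 0.753 / 0.765 | 0.751 / 0.775 |
| Any trend against TEAM (Z1 < 0) | 0.797 / 0.799 / 0.800 | 0.806 / 0.809 |

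A futility stop alone does not raise type I error.

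**6. Which reading does the text support?** The heading names a safety review plan, and the remit quoted above lists safety, adverse events, conduct and progress. Point (4) is a topic for the annual report. It is not a decision rule and is not tied to the interim. It speaks of aims in the plural: Aim 2 has three hypotheses, and Aim 3 concerns implementation. An early result on systolic BP would not show that no more data are needed for cholesterol, HbA1c or implementation. Point (5) gives termination conditions a place, in the report that the board reviews. No sentence names an interim systolic BP test, a threshold or a second significance level.

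**The case for a change.** The best case for a change is that the safety reading is nowhere stated outright. Routine safety data already reach the board every year. The extra look is timed by outcome completion, the board also guards the scientific integrity of the project, and the termination conditions are left to a report signed by the principal investigator or a designate, so they are not fixed before data accrue. A reader of the final paper could fairly ask whether the p-value may be judged at 0.05. One sentence would settle it.

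Some of this stands. The item is thin, and an unadjusted stop at p<0.05 would matter. But the sentence usually suggested, limiting the look to safety, retention and conduct data, only writes down the reading that the section already favours and alters no figure. A formal spending boundary would be needed only if someone wanted an outcome-based stop, which the plan does not announce. Nor does every outcome-based use do damage: a p<0.001 efficacy threshold leaves type I error at about 0.050, and stopping only on an adverse trend leaves power at about 0.80. The timing also has an innocent explanation: half-way through follow-up is a natural point to review retention and safety.

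**Conclusion.** No change to the plan follows. The interim is under-described, but it does not conflict with the sample size paragraph. Read as a safety and conduct review, as its heading and remit indicate, it leaves two-sided 0.05, power 0.80 and N=246 as they are.

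The possible harm is conditional: type I error of about 0.064 to 0.083 under an unadjusted p<0.05 efficacy stop, or power of about 0.74 to 0.77 under a 20% conditional-power futility stop. Both rest on thresholds that the documents do not contain, on information fractions of 0.50 to 0.667, and on a single-contrast test. The final analysis can be run and judged at 0.05 as planned. The conclusion would differ only if the board had in fact been able to stop the trial on systolic BP by arm, and nothing in the documents says so.
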